3.2 DRUG ADMINISTRATION

Appendix B-Model chemotherapy note provides a sample chemotherapy note describing the regimen.

3.2.1 Tofacitinib

Tofacitinib will be administered orally twice daily on days 1 -10 of each cycle by the participant while at home and by nursing if the participant is admitted to the inpatient unit. A diary (see **Appendix C**- Patient Medication Diary) will be kept to document dose, date and time of day the drug was dosed. If a participant vomits after taking tofacitinib, then no action is required; the participant should simply take the next dose of tofacitinib as scheduled. If a participant omits/ skips a dose, the participant should take the dose as soon as possible and contact the study team for instruction on when to administer the next dose.

3.2.1.1 VTE prophylaxis for patients receiving tofacitinib

VTE prophylaxis will be provided to all patients on study who are not already on treatment with appropriate anticoagulant (note that Vitamin K inhibitors are NOT considered appropriate therapy in this patient population) as per criteria below:

Patients with Khorana Score < 2 will receive enoxaparin 40 mg subcutaneous daily beginning Day 1 and continuing until 24 hrs after the last dose of tofacitinib for each cycle (Day 11 unless tofacitinib is discontinued early). Patients with contraindication to enoxaparin (e.g. prior history of heparin-induced thrombocytopenia or inability to perform subcutaneous injection) may instead receive another regimen (see Table 10).

Patients with Khorana Score ≥ 2 (including all pancreatic cancer and extrahepatic cholangiocarcinoma patients) will be initiated on prophylactic anticoagulation therapy throughout treatment (from Cycle 1 Day 1 until 14 days post the last dose of the study medications tofacitinib and LMB-100) as per ASCO guidelines (35). List of appropriate therapies for prophylaxis that are on CCR formulary are shown below in Table 10. Choice of therapy should be based upon patient preference, concurrent medications, bleeding risk/ tumor type, renal function, and ability to take and digest oral medication.

Table 10: Prophylaxis for VTE in Ambulatory Cancer Patients Receiving Outpatient or Inpatient Systemic Therapy (Khorana Score ≥ 2)

enoxaparin	40 mg subcutaneous injection once daily
rivaroxaban	10 mg by mouth once daily
apixaban	2.5 mg by mouth twice daily

3.2.2 LMB-100

The qualified health care professional responsible for dispensing the study drug will prepare the correct dose according to the cohort or group allocation of each participant.

LMB-100 will be given as a ~30-minute infusion on days 4, 6 and 8 (QOD x3) each 21-day cycle.

LMB-100 must be administered in a hospital or clinic equipped for IV chemotherapy. Full emergency resuscitation facilities should be immediately available, and participants should be under close supervision of the investigator or delegate at all times. For this study, participants will be admitted to the NIH Clinical Center for LMB-100 administration.

The compatibility and stability of the active ingredient was tested under simulated preparation/administration conditions.

3.2.2.1 General Instructions

- 1. LMB-100 drug product should be inspected visually for particulates prior to administration.
- 2. Do not use the solution if there is particulate matter or if it is discolored.
- 3. Do not shake or freeze the vial contents.
- 4. Ensure the drug vial content is protected from light during preparation and administration (ambient light conditions are acceptable but avoid exposure to direct sunlight).
- 5. LMB-100 drug product does not contain any preservatives. Vials are for single use only and partially used vials must not be reused.
- 6. Any unused product should be kept for drug reconciliation.
- 7. No dilution of LMB-100 drug product into 0.9% saline bags should be performed.
- 8. Do not administer as IV push or bolus.
- 9. Other drugs that require parenteral co-administration (if applicable) should be delivered via separate infusion lines and at separate infusion sites and should not be mixed with the study drug.
- 3.2.2.2 Specific Instructions

LMB-100 is diluted with 0.9% Sodium Chloride Injection, USP (0.9% NaCl) **in-line** immediately prior to administration (see **Figure 10** below).

The undiluted LMB-100 drug product (DP) is administered by intravenous infusion using a disposable syringe and syringe driver pump. So as not to compromise drug product physicochemical stability, dilution with 0.9% NaCl will be done **in-line**, immediately prior to administration of the neat DP.

In order to allow **in-line dilution (1:10) immediately prior** to administration of neat drug product, a side flow with 0.9% NaCl must be applied (as illustrated in **Figure 10**).

The pump used to administer 0.9% NaCl will be programmed at 9-times the hourly rate of LMB-100 in order to deliver LMB-100 at a concentration of 0.1 mg/mL. An IV infusion pump and syringe driver should be used to control the infusion rates for 0.9% NaCl solution and LMB-100, respectively.

LMB-100 is administered either peripherally or centrally through a patient's vascular access device. If there is no pre-existing central vascular access device and peripheral access is inadequate, a central access device will be installed.

- 1. The syringes for administration must be prepared under appropriate aseptic conditions as LMB-100 drug product does not contain antimicrobial preservatives. All preparation should be conducted within a biological safety cabinet with appropriate personal protective garb to contain and minimize exposure to the drug product under conditions of inadvertent release.
- 2. Transfer from LMB-100 product vials to a syringe a volume of LMB-100 appropriate for a patient's dose *PLUS* 3 mL excess volume to prime the extension tubing and filter set that will be attached to the syringe (see step 3).
- Attach to the syringe (first) an extension tubing set (e.g., medex REF MX448HL60) and (second) a filter set with pore size within the range of 0.2- to 0.22-μm (e.g., medex REF MX448HF). The syringe with extension set and filter set attached is "the syringe assembly".
- 4. Prime the syringe assembly tubing with LMB-100 from the syringe and cap it with a closing cone/stopper (e.g., Spinning Spiros® connector or comparable closed system transfer device cap).
- 5. The syringe assembly should be stored under refrigeration (2°-8°C; 35.6° 46.4°F) until it is used.
- 6. Chemical and physical in-use stability for LMB-100 drug product in syringes has been demonstrated for 24 hours at 2°-8°C and 24 hours at ambient temperature (not >25°C; 77°F). The LMB-100 drug product does not contain antimicrobial preservatives; LMB-100 solution will be transferred to syringes under appropriate aseptic conditions and should be used immediately. If not used immediately, total in-use storage times of prepared syringes for infusion should not exceed 24 hours when stored under refrigeration.
- 7. Attach (spike) the 0.9% NaCl container (bag) with an administration set. Attach the distal end of the administration set to the most distal port on a 4-way stopcock (or two 3-way stopcocks connected end-to-end), and prime the tubing and stopcock with 0.9% NaCl.
- 8. Attach the stopcock to the patient's vascular access device.
- 9. Undiluted LMB-100 will be filtered during administration before it is diluted in-line with 0.9% NaCl (see Figure 10). Place the syringe containing LMB-100 in the pre-programmed syringe driver, remove any caps or closures from the end of the syringe assembly and attach the syringe assembly tubing to the stopcock/manifold at the port closest to a patient's vascular access device.
- 10. Start the pump driver for 0.9% NaCl to establish line patency and unimpeded flow BEFORE starting to administer LMB-100 with the syringe pump.
- 11. When 0.9% NaCl flow is established, start the syringe pump to administer LMB-100.
- 12. The end of infusion is defined as the time point at which the syringe driver finishes administering the total volume of LMB-100 to be infused.
- 13. In case of any adverse events related to the infusion, please refer to the specific recommendation described in Section **3.3.1**.

14. The line for drawing blood for LMB-100 PK samples should be placed in the opposite extremity from the one with the infusion line in patients who do not have a mediport.

3.2.2.3 Monitoring

Vital signs (including, if possible, supine diastolic and systolic blood pressure, pulse rate, and temperature) must be monitored pre-infusion, every 15 minutes (\pm 5 minutes) until the end of the infusion, and at 30, 60 and 120 minutes (\pm 15 minutes) from the end of the infusion (EOI). Vital signs pre-infusion, EOI, and 120 minutes post-EOI must be captured in the eCRF. Other vital signs measurements are not required to be captured in the eCRF unless abnormalities are observed.

3.2.2.4 Standard Pre-medication for Participants Receiving LMB-100

Due to the prevalence of infusion related reactions (IRRs) seen in previous studies of LMB-100, all patients will be pre-medicated prior to each LMB-100 administration with the following medications:

- Diphenhydramine 25-50 mg PO or IV
- Ranitidine 150 mg PO
- Acetaminophen 650 mg PO

Dexamethasone 8 mg IV PRN (when necessary) should be physically available in the infusion unit in case of severe IRR during LMB-100 administration.

Note: An alternative histamine H2 antagonist may be substituted for PO ranitidine such as IV ranitidine or famotidine 20 mg PO or IV if the preferred pre-medication is unavailable.

Pre-medication should be given 30-60 minutes prior to LMB-100 infusion.

3.2.2.4.1 Additional Precautions for administration of LMB-100 in patients with IRR during LMB-100

Participants receiving LMB-100 who have experienced an IRR of Grade 2 to 4 during a previous infusion despite standard pre-mediation should also receive:

• Dexamethasone 8 mg IV, or equivalent dose of another corticosteroid as clinically indicated

(See Section **3.3.1** for complete instructions on response to IRRs)

Participants who experienced an IRR of Grade 3 or 4 where dexamethasone or another steroid was pre-administered should not receive further LMB-100 and will be discontinued from study therapy.

	Dose (mg)	Route
Acetaminophen	650	РО
Diphenhydramine	25-50	PO or IV
Ranitidine [#]	150	РО
Dexamethasone*	8	IV

[figure not shown]
Table 11. Pre-medications for LMB-100

*Given only in case of prior IRR

[#] IV ranitidine or famotidine 20 mg PO or IV are allowed if the preferred pre-medication is unavailable.

3.2.3 Schematic view of the administration set-up

3.3 DOSE MODIFICATIONS

3.3.1 LMB-100

LMB-100 infusion may be held for up to 48 hours due to drug-associated toxicity or adverse events from other intercurrent medical conditions (such as primary cancer diagnosis) that resolve with or without medical intervention to grade 1 or less within this time frame. Toxicities for which further LMB-100 treatment should NOT be given are stated below in **Table 12**, which also provides guideline on how to manage some toxicities anticipated with LMB-100.

Event	Action to Be Taken
IRR/hypersensitivity reaction during administration of LMB-100	If an IRR/hypersensitivity develops, the infusion of LMB-100 should be temporarily interrupted. The participant should be monitored until complete resolution of the symptoms and treated as clinically indicated. Treatment or concomitant medication may include IV saline, oxygen, bronchodilators, corticosteroids, and vasopressors depending on the symptoms.
	 If the infusion is interrupted: In the event of IRR CTCAE Grade1, upon resolution of symptoms, the infusion will resume at the rate being used at the time that the IRR occurred In the event of IRR Grade 2 or 3, upon resolution of symptoms, the infusion will resume at one-half the previous rate. In the event of IRR CTCAE Grade 3 or Grade 4 (which may include pulmonary or cardiac events) or an anaphylactic reaction, the infusion should not be restarted, and the participant should receive aggressive treatment Participants experiencing IRR CTCAE Grade 4 or anaphylaxis must be permanently discontinued from study treatment For participants receiving LMB-100 who previously experienced IRR CTCAE ≥ Grade 2, the infusion rate for subsequent LMB-100 infusion should be reduced to one-half of the previous rate and corticosteroids premedication should be given 30 minutes prior to infusion in addition to standard pre-medications: Dexamethasone (20 mg PO 6 -12hrs before infusion or 8
	mg IV, $30 - 90$ min before infusion) or equivalent dose of another corticosteroid as clinically indicated
Capillary leak syndrome (CLS)	In the event of Grade 4 CTCAE capillary leak syndrome (urgent intervention indicated):
For Grade 1-3 Capillary leak syndrome, the symptoms that make up this syndrome will be recorded separately, instead of classifying them as CLS.	 Vasopressor support (e.g., phenylephrine) if indicated to stabilize blood pressure Administer colloidal solutions (e.g., albumin) if there is a clinically significant, symptomatic and persistent systolic blood pressure drop, urine output significantly declines, or serum albumin falls to 2.5 mg/dL or lower
If the PI determines that the symptoms meet the definition of Grade 4 or 5 CLS, they will be recorded separately and CLS Grade 4 or 5 will also be recorded.	 For pulmonary congestion provide diuretic and/or albumin treatment as appropriate Progressive shortness of breath may require endotracheal intubation or drainage of a pleural effusion For oliguria and /or rising serum creatinine level delay LMB-100 if Grade 3 urine output decrease (<10 mL/hr)

Table 12. Guidelines for Managing LMB-100 Adverse Events

Event	Action to Be Taken			
	• Use dopamine if participant is unresponsive to or unable to tolerate fluids			
	• Manage pericardial effusion as outlined in section on "Inflammatory reactions to serosal membranes" below			
Inflammatory reactions to serosal membranes	 Hydrocortisone (200 mg IV) or a glucocorticoid equivalent as clinically indicated 			
	 o In the event of Grade ≥2 CTCAE pericardial effusion (asymptomatic effusion small to moderate size), consider delaying LMB-100 administration. In the event of Grade ≥3 CTCAE pericardial effusion (effusion with physiologic consequences) permanently discontinue LMB-100 treatment. Consult cardiology service for management recommendations which may include pericardial drainage. 			
	• In the event of pleuritis resulting in mild to severe pleuritic pain, treat with analgesics or steroids as clinically indicated			
	 For participants who have previously experienced pleuritis consider administration of dexamethasone 4 mg, PO bid beginning with first LMB-100 infusion and completing 24 hours after the last LMB-100 infusion of the cycle. (If participant is already receiving corticosteroids at dose and schedule at or above this amount as part of the pre-medication regimen, do not give additional steroids for pleuritis) 			
Dehydration	Encourage participants to maintain oral hydration (~1.5 L/ day)			
Nausea	Ondansetron or another anti-emetic should be available as needed			
Renal toxicity	In the event of Grade 1 or greater renal toxicity consider increasing oral or intravenous hydration, and consider delaying LMB-100 administration by up to 48hrs.			
	In the event of Grade 2 or greater renal toxicity hold LMB-100 administration until recovery to Grade 1 or better. If this does not occur within 48hrs, no further LMB-100 should be given during the cycle.			
IRR = infusion related reaction; IV =	= intravenous; CTCAE = Common Terminology Criteria for Adverse			

Events

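### Table 12 tells staff both to resume at half rate and not to restart after a grade 3 infusion reaction, and nothing settles it for patients without steroid pre-medication

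*Combined protocol and SAP*

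**What the plan says.** Section 3.3.1 presents Table 12 as the controlling text: "Toxicities for which further LMB-100 treatment should NOT be given are stated below in" that table. Section 3.2.2.4.1 likewise refers the reader to section 3.3.1 "for complete instructions on response to IRRs", and section 3.1.1 points to section 3.3 for the precautions to take after an IRR of grade 2 or worse.

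For an infusion that has been interrupted, Table 12 says:

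- Grade 1: resume at the same rate.
- Grade 2 or 3: "In the event of IRR Grade 2 or 3, upon resolution of symptoms, the infusion will resume at one-half the previous rate".
- Grade 3, grade 4 or anaphylaxis: "IRR CTCAE Grade 3 or Grade 4 (which may include pulmonary or cardiac events) or an anaphylactic reaction, the infusion should not be restarted".
- Grade 4 or anaphylaxis: permanent discontinuation.

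A separate bullet governs later infusions in patients "who previously experienced IRR CTCAE ≥ Grade 2, the infusion rate for subsequent LMB-100 infusion should be reduced to one-half of the previous rate", with steroid pre-medication added.

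Outside the table, section 3.2.2.4.1 says: "Participants who experienced an IRR of Grade 3 or 4 where dexamethasone or another steroid was pre-administered should not receive further LMB-100". Section 3.2.2.4 says "all patients will be pre-medicated prior to each LMB-100 administration with the following medications", and then lists an antihistamine, an H2 blocker and acetaminophen. Dexamethasone appears in Table 11 with the footnote "Given only in case of prior IRR".

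**The concern.** Grade 3 is named in two adjacent bullets with opposite actions. Whichever one bedside staff follow, they depart from the other. The decision is whether to re-expose a patient to the provoking drug shortly after a severe reaction, so it should not depend on which line is read first.

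The dose-limiting toxicity (DLT) rule is no backstop, because section 3.1.1 excludes IRRs up to grade 3 from the DLT definition. Table 12 is the operative control.

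The statistical stake is small. A stopped infusion need not lose the cycle 2 endpoint: section 5.2 samples the end of infusion on days 4 and 8, and section 10.1.1 counts any administration in the cycle. Inconsistent handling could, however, change which escalation patients count as evaluable for DLT.

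**Working it through.** The check is mainly textual.

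**1. Grades covered by each rule**

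| Rule in Table 12 | Grades | Action on the interrupted infusion |
|---|---|---|
| Half-rate bullet | 2, 3 | Resume after symptoms resolve |
| No-restart bullet | 3, 4, anaphylaxis | Do not restart |

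The overlap is exactly grade 3. Neither rule mentions steroid pre-medication.

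**2. Could other text settle the overlap?**

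- *The half-rate bullet might be meant for later infusions.* It is not. A separate bullet covers later infusions, and both conflicting bullets sit under the heading for an interrupted infusion.
- *The remark on pulmonary or cardiac events might split grade 3 into two kinds.* It only says what the reaction may include and sets no condition.
- *The permanent-discontinuation bullet.* It covers grade 4 and anaphylaxis only.
- *Section 3.2.2.4.1.* It stops further LMB-100 after grade 3 or 4 where a steroid was pre-administered. That settles the steroid case and no other.
- *The 48-hour hold in sections 3.3.1 and 3.3.3.* It permits a delayed dose. It does not say whether an infusion stopped for a grade 3 IRR is restarted.
- *Section 12.1.2.1.* It asks for supportive care and monitoring until resolution.
- *Section 3.1.1.* It refers the reader back to section 3.3.

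The unsettled case is therefore a grade 3 IRR without steroid pre-medication. Because standard pre-medication has no steroid, a first reaction of grade 3 on the standard regimen normally falls there.

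**3. How often might grade 3 IRRs occur?**

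Inputs: 1 grade 3 IRR in 13 patients (Table 3, section 1.2.8.1.1); at most 27 evaluable patients, of whom up to 12 are in escalation; a ceiling of 45 (section 10.2).

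- Rate: 1/13 = 0.0769. Exact (Clopper-Pearson) 95% CI: 0.00195 to 0.3603.
- Chance of at least one in 27, from 1 − (1 − p)^27:
  - lower limit: 1 − (1 − 0.00195)^27 = 0.051
  - point estimate: 1 − (12/13)^27 = 0.885
  - upper limit: 1 − (1 − 0.3603)^27 = 0.99999
- Expected number in 27, from 27p: 0.05, 2.08 and 9.73.
- Expected number in 12 escalation patients, from 12p: 0.02, 0.92 and 4.32.
- Places above the evaluable maximum: 45 − 27 = 18.

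These figures count every grade 3 IRR, not only the unsettled ones. The documents do not say whether the one affected patient had received a steroid.

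**The case against.** The strongest reply accepts the overlap and disputes how much it matters.

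- **The open zone is narrow.** It is one grade, within one infusion, without a prior steroid. Grade 4, anaphylaxis, the steroid case and later infusions all have clear rules. This is correct.
- **Safeguards are strong.** The infusion is interrupted and the patient watched until symptoms resolve completely. Dosing is inpatient with resuscitation facilities, vital signs are taken every 15 minutes, and dexamethasone is on the unit. A cautious clinician can simply not restart. All this lowers the likely harm, but none of it states the rule.
- **Table 12 is called a guideline.** That softens the tone but does not remove the contradiction. Other sections rely on the table as the full instruction.
- **The earlier experience was mild.** Section 1.2.8.1.1 describes 8 IRRs in four patients as non-serious and gone within about an hour, with pre-medication before later doses. The same section lists IRR among the serious adverse events and Table 3 shows one of grade 3, so the source is not consistent. The absence of IRRs in 15 long-infusion patients (section 1.2.8.2.3) comes from a different schedule.
- **The rate figures say little.** One event gives an interval too wide to be useful. That trial began without pre-medication, whereas every patient here receives it. IRR is associated with antidrug antibodies, which tofacitinib is meant to suppress. The 27 is also a maximum, since eligible escalation patients treated at the maximum tolerated dose may count towards the 15. This stands: the figures show plausible scale only.
- **A first IRR can occur with a steroid on board**, for example in a patient given dexamethasone for earlier pleuritis (Table 12). This also stands, but such a patient falls under the steroid rule and outside the group at issue.

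**Conclusion.** The concern holds. For a grade 3 IRR in a patient not pre-medicated with a steroid, Table 12 gives contradictory instructions about the same infusion, and no other section sets a precedence. The conclusion rests on the wording alone and needs no assumption about rates.

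It should be corrected before the table is relied on, because it concerns re-exposure after a severe reaction and wording alone can fix it. If the earlier trial's rate carried over, about 2 of 27 patients would have a grade 3 IRR (0.05 to 9.7 over the confidence interval). The unsettled subset may be smaller. The design's error rates, power and sample size are unaffected.

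**What to change.** Name grade 3 in one Table 12 bullet only.

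**Safer default, for the sponsor to confirm:** remove grade 3 from the half-rate bullet. The ladder then reads: grade 1, same rate; grade 2, half rate; grade 3, no restart that day, with later infusions at half rate under steroid cover where section 3.2.2.4.1 allows; grade 4 or anaphylaxis, permanent discontinuation.

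**If restart after grade 3 is intended:** remove grade 3 from the no-restart bullet, and state in the half-rate bullet that a grade 3 reaction after a pre-administered steroid is excepted, to match section 3.2.2.4.1. The documents do not show which was meant.

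**Optional tidy-up:** limit the prior-IRR pre-medication text in section 3.2.2.4.1 and Table 12 to grades 2 and 3, since grade 4 is permanently discontinued. Nothing above depends on it.

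**Cost of the default:** one bullet is reworded. A patient with a grade 3 IRR does not complete that day's infusion. In cycle 1 of escalation that patient may fail the section 10.3.1 requirement to receive every dose, and may need replacing. At the earlier rate this is about 0.9 of 12 patients (0.02 to 4.3), and fewer if some reactions come after cycle 1. The 18 places above the evaluable maximum are available for this but are shared with screen failures and others who do not complete the DLT period.
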